Random assignment to the treatment will be conducted at the ECDC level (n=19). We eliminated one of these ECDC because it did not provide the infrastructure required to run the group sessions – a private space. However, this center is not different than the other 18 ECDC over a range of observable characteristics. Out of the remaining 18 ECDC, we conducted a random assignment based on the ECDC's size, age-range, gender and anthropometrics of eligible children, the size of the center, and a composite socio-economic status score. In doing so, 9 ECDC were selected to run the implementation, while the other 9 remaining centers were assigned to the control arm.

Within each center assigned to the treatment arm in each cohort, the total number of families invited to participate in the program, and the number of intervention groups, will be based on the number of children served by the center relative to the total number of children served by the 18 ECDC in Tumaco. Then, we will distribute the treated ECDC and intervention groups across the 4 cohorts, ensuring that each ECDC has at least one intervention group per year. Hence, larger ECDC in the treatment arm will have one or more intervention groups in each of the 4 cohorts, whereas the smaller ECDC will have at least one intervention group in 2018 and another one in 2019.

For each treated ECDC in each cohort, we will randomly order eligible subjects within each center to be invited to participate in the intervention and invite them to participate according to this ordered list. Invitations will be carried out by the team of six social workers starting three weeks prior to the start of the intervention. Eligible subjects will be contacted at the ECDC or by phone and will be informed of the objectives and structure of the program, the schedule of the group sessions, and the potential benefits, including small incentives (super market cash cards or other incentives for up to US\$8) for completing each phase of the data collection.

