- 40 groups of 16 participants in treatment and 640 participants in the control arm. (n = 1280)

- **Minimum detectable effect size for main outcomes (accounting for sample design and clustering)**

With 1280 participating households, nested in 18 child development centers, half of which are randomly assigned to an implementation cohort of the program, we estimate to have 80% of power to detect effect sizes ranging from 0.262 to 0.2221 at minimum. This range of minimal detectable effect sizes (MDES), is based on estimates in which we define a 0.05 probability of type I error, assign 9 clusters and half of the individual-level sample (640) to the treatment, and employing two-tailed tests in all our estimations. For all our estimations, we assume an Intra-class correlation coefficient (ICC) of 0.04, based on pilot estimations and a review of the literature. All power calculations were conducted with Power-Up! (Dong & Maynard, 2013), and validated using EGAP's Online Power Calculation Tool.

The smaller estimated MDES assumes that no covariates will be used in the estimation models, which would account for 30% of outcome variability explained by demographic covariates. Considering the range of effect sizes observed in the pilot evaluation, we consider that this study is adequately powered to detect smaller effects sizes than those previously reported. Assuming an attrition rate of 8%, the effective sample, we still be powered to detect effect sizes of 0.27. Telephonic check-ups and small incentives will be used to minimize attrition.

Note: Security conditions have worsened in Tumaco, leading to some uncertainty regarding our ability to implement the program in 2019. In this extreme case, the trial would only be run over the two 2018 cohorts, with 640 participating households, nested in 18 child development centers, half of which are randomly assigned to an implementation cohort of the program. In such case, we estimate to have 80% of power to detect effect sizes ranging from 0.341 to 0.405 at minimum. This range of minimal detectable effect sizes (MDES), is based on the same estimates as above: 0.05 probability of type I error, 9 clusters and half of the individual-level sample (320) assigned to the treatment, two-tailed statistical tests in our estimations and an Intra-class correlation coefficient (ICC) of 0.04. If we account for covariates, and assuming an attrition rate of 8%, we be powered to detect effect sizes of 0.404.

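### The four-cohort minimum detectable effect (0.262 to 0.2221) is smaller than its own inputs give, and it states no allowance for the unequal centre sizes the design builds in

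*Protocol*

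**What the plan says.** Under Experimental Design Details, the number of families and groups in each treated centre follows that centre's share of all children served by the 18 centres. At the low end, "the smaller ECDC will have at least one intervention group in 2018 and another one in 2019". At the high end the rule is more generous: "larger ECDC in the treatment arm will have one or more intervention groups in each of the 4 cohorts". The control centres follow a similar rule, so sizes differ within both arms.

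The section on the minimum detectable effect size says in its heading that the figure accounts for sample design and clustering. The inputs it lists are:

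- "With 1280 participating households, nested in 18 child development centers"
- "assign 9 clusters and half of the individual-level sample (640) to the treatment"
- "we define a 0.05 probability of type I error", "employing two-tailed tests in all our estimations"
- "we assume an Intra-class correlation coefficient (ICC) of 0.04"
- covariates explaining 30% of outcome variability, with the level (centre or individual) not stated

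The result is: "we estimate to have 80% of power to detect effect sizes ranging from 0.262 to 0.2221 at minimum". With 8% attrition the section gives 0.27. If only the 2018 cohorts run (640 households, the same 18 centres), it gives 0.341 to 0.405. It gives no centre sizes, no CV of centre size and no allowance for size variation. It does not say that equal sizes were assumed either.

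**The concern.** With only 18 centres and about 71 households in each, the between-centre component makes up most of the variance of the treatment effect. Variation in centre size inflates that component, so an MDES that leaves it out is optimistic. The protocol uses its MDES to conclude that the trial is adequately powered compared with effects seen in the pilot. If the figure is too small, a reader will credit the trial with 80% power for effects that it detects less often.

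**Working it through.** **Inputs** (all from the MDES section): J = 18 centres, 9 per arm; N = 1280; ICC = 0.04; two-sided alpha 0.05; power 80%; R² = 0.30 where covariates are used. Mean centre size is m = 1280/18 = 71.1.

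**Formula.** MDES = M × √[DEFF × (1 − R²) / (0.25 N)]. M is the sum of the 97.5% and 80% points of t with 16 df: 2.120 + 0.865 = 2.985.

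**Step 1: the plan's own figure, equal centres.** DEFF = 1 + (71.1 − 1) × 0.04 = 3.80.

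- No covariates: 2.985 × √(3.804/320) = **0.325**, against 0.262 stated.
- R² = 0.30 at both levels: 0.325 × √0.70 = **0.272**, against 0.2221 stated.
- A normal multiplier (2.802) in place of t gives 0.306 and 0.256, still above the stated values.
- With infinitely large equal centres, the no-covariate MDES is 2.985 × √[0.04/(0.25 × 18)] = 0.281 (normal 0.264). No centre size therefore reaches 0.262 without covariates.

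This takes the larger stated value as the one without covariates. The protocol words it the other way round. Read literally, the no-covariate figure would be 0.2221 and the gap wider.

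At a true effect of 0.262 without covariates, power with equal centres is about 62%, not 80%.

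**Step 2: unequal centres.** Centre sizes are not given, so the CV is assumed. The Intervention(s) section implies 42 groups (9 + 9 + 12 + 12); elsewhere the protocol says 40. The patterns below spread 42 groups over 9 treated centres, scale each arm to 640 people and give both arms the same pattern.

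Two variance formulas apply, depending on the estimator:

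- Individuals equally weighted: DEFF = 1 + [(1 + CV²)m − 1] × ICC.
- Centres weighted efficiently, as in a mixed model: information per arm I = Σ n_j / [1 + (n_j − 1) × ICC], and MDES = M × √(2/I).

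| Illustrative pattern | CV | Size-weighted | Equally weighted |
|---|---|---|---|
| all equal | 0 | 0.325 | 0.325 |
| 2 centres with 3 groups, 7 sharing 36 | 0.19 | 0.327 | 0.330 |
| 3 centres with 2 groups, 6 with 6 | 0.40 | 0.333 | 0.345 |
| 5 centres with 2 groups, 4 with 8 | 0.64 | 0.341 | 0.372 |

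Last row in full: two groups scale to 30.5 people and eight to 121.9. Then I = 5 × 30.5/2.179 + 4 × 121.9/5.836 = 153.5, and 2.985 × √(2/153.5) = 0.341. Equally weighted, DEFF is 4.97 and 2.985 × √(4.97/320) = 0.372.

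Relative to 0.325 the increase is about 1% to 5% size-weighted and about 2% to 14% equally weighted. In the last row, power at an effect of 0.325 falls from 80% to about 76% and 69% respectively.

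**Step 3: attrition.** With 8% loss (N = 1177.6), equal centres give 0.329 without covariates and 0.275 with R² = 0.30. The stated 0.27 is just below the second, so it shows no room for size variation.

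**Step 4: 2018 cohorts only.** N = 640, m = 35.6, DEFF = 1 + 34.6 × 0.04 = 2.38. The MDES is 2.985 × √(2.382/160) = 0.364 without covariates and 0.305 with R² = 0.30. Both are below the stated 0.405 and 0.341. Under the equally weighted formula the stated values correspond to a CV of about 0.63 to 0.65.

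**The case against.** A reader might infer that the calculation treated the 18 centres as equal and that this is why the MDES is too small. The documents do not support that. The protocol is silent on sizes, and equal centres do not reproduce its figures, so they cannot be shown to rest on an equal-size assumption. Going from 0.262 to 0.325 is a 24% increase that arises before any size variation enters.

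The amount added by unequal sizes is also open to challenge. The recruitment rule sets only minimums. It fixes neither a largest centre nor the number of small ones, so every CV above is illustrative. The upper figures (0.372, power 69%) need both the most uneven pattern and an equally weighted analysis. The protocol does not fix the estimator, and an efficiently weighted one loses at most about 5% over the range shown.

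Nor can the 2018-only figures be called too small, since they exceed the equal-centre values.

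All of this stands. It limits what can be attributed to unequal size, but it does not rescue the stated four-cohort figure. At fixed N, number of centres and ICC, unequal sizes cannot lower the MDES. Randomising on centre size may balance the arms, but it leaves the variation within each arm.

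**Conclusion.** The four-cohort MDES is wrong as written. On the protocol's inputs, with t on 16 df, it is about 0.325 without covariates and 0.272 with R² = 0.30 at both levels, against 0.262 and 0.2221 stated. Placing R² at both levels is an assumption, and the favourable one: placing it at one level only gives 0.287 or 0.313.

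Unequal centre size is a second, smaller gap in the same calculation. The design builds it in and the listed inputs make no provision for it. For an assumed CV of about 0.2 to 0.64 it takes the no-covariate value to about 0.327 to 0.341 (size-weighted) or 0.330 to 0.372 (equally weighted). Its true size cannot be fixed from the protocol. The 2018-only range is not shown to be in error on this count.

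**What to change.** Recompute and restate the four-cohort MDES from the listed inputs. Use the actual centre counts in the partner's administrative data, which already serve to select participants, and a variance formula that matches the planned estimator. State the CV and the R² used, and the level at which R² applies. Recompute the attrition and 2018-only figures on the same basis for consistency.

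The cost is one recalculation and a less favourable stated figure. Recruitment does not change.

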Participants will be selected two to three weeks prior to the starting date of the program. Selection will be based using administrative data from Genesis Foundation. We will use this information to randomly assign a total of 640 mothers or primary care givers into the program and 640 into a control group. Participants will be assigned to a 16-member group intervention group in the ECDC closest to their residence. Groups will meet once per week for approximately 3 hours per session.

Subjects assigned to the control group, and those in centers assigned to the intervention but not randomly selected to participate in the program, will continue benefiting from the services available to all families affiliated with child development centers in the municipality of the intervention.

Due to local operation and implementation restrictions, the program will be delivered in four sequential cohorts of approximately 160 participants in the intervention arm and 160 participants in the control arm per cohort. The total number of intervention groups will vary per cohort starting with 9 groups in each of the two cohorts of 2018 and increasing to 12 groups for each of the two cohorts in 2019. After the implementation of these four sequential cohorts, we will reach 640 participants in the intervention arm, and 640 subjects in the control arm.

The implementation of the program will be led by a team of six social workers who participated in a three-week intensive training. The team of trained social workers will be assigned into three dyads. Each dyad will lead the implementation of the program among 3 to 4 groups per cohort and complete implementation and debriefing logs on the progress of the session and the participants. The implementation team, in addition, will be supervised by three expert coaches on a weekly basis. The supervision scheme aims to guarantee the quality and fidelity of the intervention but also to provide reflexive support to mitigate burn-out and symptoms of vicarious trauma.

To ensure adherence, we will implement the following actions: First, sessions will be held during a day and time convened with the participants. Second, community health workers will make weekly phone calls to follow-up on each participant's needs and progress and encourage attendance. We followed this strategy during the implementation pilot and observed that 94% of the mothers who participated in the program completed all the sessions.

- **Outcomes (End Points)**

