Eligible subjects will also be informed that their decision to participate or not in *Semillas de Apego* and the data collection does not have any consequence on access to Genesis Foundation's programs in the municipality, including their children's access to the ECDC, or their participation in standard community groups and activities. Once eligible subjects accept to participate, they will be contacted by the data collection firm, which will coordinate the date and time of the baseline data collection.

We will follow a similar strategy in the ECDC assigned to the control arm. We will first calculate the number of families that were invited to participate in the program based on the number of children served by the center relative to the total number of children served by the 18 ECDC

in Tumaco. Then, we will distribute the ECDC across the 4 cohorts, ensuring that in each ECDC we assemble control groups at least once per year. Hence, larger ECDC in the control arm will have one or more control groups in each of the 4 cohorts, whereas the smaller ECDC will have at least one control group in 2018 and another one in 2019.

Then, we will randomly order eligible subjects within each center to be invited to participate in the different phases of data collection. Invitations will be carried out by the data collection team three weeks prior to the start of the intervention. Eligible subjects will be contacted at the ECDC or by phone and will be informed of the objectives and structure of the data collection and the potential benefits, including small incentives (super market cash cards for up to US\$8) for completing the data collection.

Eligible subjects will also be informed that their decision to participate in the data collection does not have any consequence on access to Genesis Foundation's programs in the municipality, including their children's access to the ECDC, or their participation in standard community groups and activities.

All randomization procedures will be conducted using the RANDOMIZE module (Kennedy & Mann, 2015), available in Stata 15. In doing so, we achieve balance on key characteristics at each phase of the randomization procedure.

- Randomization Unit

1st stage/level: Early Childhood Development Center. 2nd stage/level: individual - primary caregiver

- Was the treatment clustered?

Yes

- **Planned Number of Clusters**

- 18 (9 per treatment arm).

- **Planned Number of Observations.**

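### After centres are allocated, caregivers enter the two arms through different invitations, which creates a selection risk of unknown size and direction

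*Protocol*

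**What the plan says.** All of this is in the Protocol; no SAP was available.

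- **Allocation comes first.** Experimental Design Details reports it as done: "9 ECDC were selected to run the implementation, while the other 9 remaining centers were assigned to the control arm".
- **Treated centres.** Eligible caregivers are put in random order and invited to the intervention. "Invitations will be carried out by the team of six social workers starting three weeks prior to the start of the intervention". They are "informed of the objectives and structure of the program, the schedule of the group sessions, and the potential benefits". Then: "Once eligible subjects accept to participate, they will be contacted by the data collection firm", which arranges the baseline. Under Intervention(s), "The implementation of the program will be led by a team of six social workers", so on the natural reading the inviters also deliver the programme.
- **Control centres.** "We will follow a similar strategy in the ECDC assigned to the control arm". Caregivers are again randomly ordered, but here "to be invited to participate in the different phases of data collection". The inviting is done by the data collection team, also three weeks ahead, and caregivers are told about the data collection only.
- **A different account.** Intervention(s) describes random assignment of eligible individuals, 640 to the programme and 640 to control. It also refers to caregivers in intervention centres who were not randomly selected for the programme.

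**The concern.** What a caregiver must accept in order to enter the sample depends on the arm. In a treated centre it is 15 weekly sessions of about 3 hours (15 × 3 = about 45 hours) plus the surveys. In a control centre it is the surveys and child assessments alone. The recruiter and the information given differ as well. All of this happens after allocation.

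Availability, motivation or distress could influence whether a caregiver accepts a long group programme. The same traits could predict the primary outcomes: caregiver mental health, child rearing, the emotional bond, and child mental health and development. If so, the enrolled arms differ for reasons unrelated to the programme, and a larger sample does not reduce that difference. Baseline covers all five constructs and a household survey, so adjustment can deal with the measured part only.

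**Working it through.** **1. What is matched and what is not**

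| Feature | Treated centres | Control centres |
|---|---|---|
| List order | random | random |
| Contact | at the centre or by phone | same |
| Timing | from three weeks before start | three weeks before start |
| No effect on access to services | stated | stated |
| Incentive | cards or other incentives, up to US$8, for each data collection phase | cards, up to US$8, for the data collection |
| Recruiter | six social workers | data collection team |
| Invited to | programme | data collection |
| Baseline | arranged after acceptance | part of what is accepted |

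For incentives only the ceiling is plainly common. The statement on balance in Experimental Design Details covers the randomization steps, not the accepted samples. The 94% under Intervention(s) is session completion among pilot participants, not acceptance of an invitation.

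**2. Scale, on assumed values**

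The protocol states no figure for selection, so there is none to reproduce. Acceptance rates and acceptor–decliner gaps below are assumptions.

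Inputs from the sample-size section: 18 centres, n = 1,280, ICC 0.04, two-sided 5%.

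SE = √(0.04×4/18 + 0.96×4/1280) = √(0.00889 + 0.00300) = 0.109, with 16 df.

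Minimum detectable effect = (2.120 + 0.865) × 0.109 = 0.325. The protocol states 0.262 to 0.2221, which this formula does not reproduce. That is a separate matter, and the point here does not depend on it.

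With a acceptance and d the acceptor-minus-decliner gap in SD:

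shift = (1 − a_T)·d_T − (1 − a_C)·d_C

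- *Mild case:* a_T = 0.80, a_C = 0.90, d = 0.2 to 0.5 in both arms. Shift = (0.20 − 0.10) × d = 0.02 to 0.05 SD.
- *Selection different in kind:* acceptance 0.80 in both arms, d_T = 0.2 to 0.5, d_C = 0. Shift = 0.20 × d_T = 0.04 to 0.10 SD.

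Two-sided rejection rate under no programme effect (noncentral t, 16 df). The adjusted rows take the protocol's 30% of variability as R² at both levels, so SE = 0.109 × √0.7 = 0.091:

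| | Mild | Different in kind |
|---|---|---|
| Unadjusted | 5.3–7.2% | 6.4–13.9% |
| Adjusted, half the shift removed | 5.1–5.8% | 5.5–8.1% |
| Adjusted, none removed | 5.5–8.1% | 7.0–17.8% |

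At the SE implied by the protocol's own 0.262 (0.262/2.985 = 0.088), unadjusted shifts of 0.02, 0.05 and 0.10 give 5.5%, 8.4% and 18.8%.

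The sign is unknown, so power can move either way. At a true effect of 0.325 (80% power), shifts of −0.05, −0.02, +0.02 and +0.05 give 66%, 75%, 84% and 90%.

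**3. Limits on the assumed acceptance**

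Filling 640 places needs 640/0.8 = 800 invitations at 80% acceptance and 640/0.6 = 1,067 at 60%. The 18 centres serve over 2,000 children aged 0 to 5, so nine hold about 1,000 if the split is even (assumption), and fewer are in the eligible age range at any one time. New intake over 2018–2019 adds to this. The pool suggests that acceptance has to be fairly high, which limits the shift but does not fix it.

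**The case against.** Much of the procedure is parallel, baseline is planned before the intervention, and the protocol calls the two strategies similar. The magnitudes are all assumed, the mild case is close to nominal, and 13.9% needs a 0.5 SD gap for the programme, none for data collection, and no adjustment. Adjustment for the baseline outcome might remove more than the demographic covariates behind the 30%. If 640 are to be enrolled from a tight pool, acceptance must be high and the shift small. All of this stands, and it is why the point is a risk and not a demonstrated bias.

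Two stronger readings are tempting. One is that treated-centre caregivers who decline the programme are never surveyed, so their outcomes are lost. The plain sequence is acceptance, then baseline, and no survey of decliners is described. But no sentence bars them from giving data, and the text treats the decision on the programme and on the data collection together. The other is that the invite-and-accept procedure is the settled design. Intervention(s) describes random assignment of individuals, including unselected caregivers in treated centres, and the two accounts are not reconciled.

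It can also be said that counts of refusals and comparisons of acceptors belong in a SAP or trial report. That is fair for the analysis. Who makes first contact, with what offer, and whether refusals are recorded are field procedures that have to be settled before recruitment.

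**Conclusion.** The concern holds as a design risk. Offer, recruiter and accepted burden differ between arms after the 9/9 allocation, and neither random list order nor the balance statement makes the acceptors comparable. Size and direction cannot be derived from the protocol. Under the assumptions shown, the effect runs from negligible (a 0.02 SD shift, 5.3% error) to material (0.10 SD, 13.9% unadjusted). No imbalance has been observed, and the documents do not support a claim that the trial is biased. The point is worth fixing because the main safeguards are cheap and because refusals that go unrecorded may not be recoverable later.

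**What to change.** For cohorts not yet recruited:

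1. The data collection firm makes first contact in all 18 centres, working strictly down the random list with a common data-collection script.
2. Reconcile Intervention(s) with Experimental Design Details on how individuals enter each arm, and state whether caregivers who decline the programme may still give data.

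In all centres:

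3. Log every caregiver invited, accepting and declining, by centre and arm.
4. Compare acceptors with decliners, and acceptors between arms, on the administrative data already held. If acceptance or composition differs, qualify the causal claim. For cohorts already recruited, this description is all that can be done, as far as records allow.

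The cost is a protocol amendment, modest extra contact work for the firm and a little more analysis. These steps reduce or expose the selection; they do not remove it, because entry to the treated sample may still depend on accepting the programme.

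**Option for the sponsor to weigh, not a required change.** Complete baseline before the programme is offered, and follow everyone with a baseline by intention to treat. This removes the differential filter, although in later cohorts caregivers may already know which centres run the programme. It has a price:

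- At assumed uptake of 90% or 80%, filling 640 places needs 640/0.9 − 640 = 71 or 640/0.8 − 640 = 160 extra caregivers. Over three assessments that is 213 or 480, and up to US$1,704 or US$3,840 at US$8 each.
- The effect is diluted to 0.325 × 0.9 or 0.325 × 0.8. Unadjusted power falls from 80% to about 71% or 61%. With R² 0.30 at both levels, and counting the extra baselines, it falls from 92% to about 86% or 77%.
- At 90% consent (assumed), it needs 711/0.9 = 790 or 800/0.9 = 889 treated-centre invitations, which the eligible pool may not support.

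In the mild case that loss of power can exceed the loss from the selection itself.

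### The stated minimum detectable effects of 0.262 to 0.2221 do not follow from 18 centres and an ICC of 0.04; the design detects about 0.33 without covariates and 0.27 to 0.31 with them

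*Protocol*

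**What the plan says.** All of this stands in the protocol section on minimum detectable effect size for main outcomes.

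- **Sample and clusters:** "With 1280 participating households, nested in 18 child development centers".
- **Allocation:** "assign 9 clusters and half of the individual-level sample (640) to the treatment".
- **Error rate and sidedness:** "we define a 0.05 probability of type I error" and "employing two-tailed tests in all our estimations".
- **Clustering:** "we assume an Intra-class correlation coefficient (ICC) of 0.04".
- **Result:** "we estimate to have 80% of power to detect effect sizes ranging from 0.262 to 0.2221 at minimum".
- **Covariates:** "The smaller estimated MDES assumes that no covariates will be used in the estimation models, which would account for 30% of outcome variability".
- **Attrition:** "Assuming an attrition rate of 8%, the effective sample, we still be powered to detect effect sizes of 0.27".

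The section concludes that the study is adequately powered relative to the pilot effects. It then gives a fallback for the 2018 cohorts alone: 640 households, the same 18 centres and the same assumptions, with a stated MDES of 0.341 to 0.405, and 0.404 with covariates and 8% attrition. The entries on experimental design and planned number of clusters confirm that centres are the first-stage randomisation unit, 9 per arm.

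**The concern.** With only 18 randomised centres, between-centre variance dominates the precision of the treatment effect, and adding families within centres helps little. An MDES of 0.22 to 0.26 looks too small for that number of centres at an ICC of 0.04. The sentence on covariates also runs against how adjustment works: covariates that explain outcome variance lower the MDES, so the smaller figure cannot be the one without them.

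This paragraph is the document's only justification of the sample size. If it is wrong, readers will credit the trial with 80% power at effects where it has much less. A null result on one of the five primary constructs could then be taken to exclude effects of 0.22 to 0.26 that the trial had a substantial chance of missing.

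**Working it through.** **Inputs, all from the MDES section:** N = 1280; J = 18 centres; half the centres and half the households treated; ICC = 0.04; two-sided alpha 0.05; power 80%; covariate R² = 0.30; attrition 8%. The level at which the 30% applies is not stated, so each possibility is shown.

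**Formula** (two-level design, treatment assigned to centres, equal allocation):

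MDES = M × sqrt[ 4·ICC·(1 − R²c)/J + 4·(1 − ICC)·(1 − R²i)/N ]

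Here R²c and R²i are the shares of centre-level and individual-level variance explained. With J − 2 = 16 degrees of freedom, M = 2.120 + 0.865 = 2.985. With the normal approximation, M = 1.960 + 0.842 = 2.802.

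**Attempt to reproduce the stated figures, N = 1280.** The centre term is 4 × 0.04/18 = 0.00889. The individual term is 4 × 0.96/1280 = 0.00300.

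| Case | Variance | MDES (t, 16 df) | MDES (normal) |
|---|---|---|---|
| No covariates | 0.01189 | 0.325 | 0.305 |
| 30% at individual level only | 0.01099 | 0.313 | 0.294 |
| 30% at centre level only | 0.00922 | 0.287 | 0.269 |
| 30% at both levels | 0.00832 | 0.272 | 0.256 |

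The stated range is 0.262 to 0.2221. No two-sided version with these inputs falls below 0.256.

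**Limit set by the centres.** Dropping the individual term (infinitely many households per centre) leaves 2.985 × sqrt(0.00889) = 0.281 without covariates, or 0.264 with the normal multiplier. The stated 0.262 is below both. With 30% explained at centre level, the limit is 0.235 (t) or 0.221 (normal). The stated 0.2221 is below the first and just above the second.

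**Power at the stated effects** (noncentral t, 16 df; normal in brackets):

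- 0.262, no covariates: 62% (67%).
- 0.2221, 30% at individual level: 51% (56%).
- 0.2221, 30% at both levels: 63% (68%).
- 0.2221 read literally as the no-covariate figure: 48% (53%).

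**What would be needed.** To reach 0.262 without covariates takes an ICC of about 0.021, or about 31 centres sharing the same 1280 households. To reach 0.2221 takes R² of about 0.53 at both levels, since (0.2221/0.3254)² = 0.466.

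**After 8% attrition,** N = 1280 × 0.92 = 1177.6. The t-based MDES is 0.329 without covariates, 0.315 with 30% at individual level and 0.275 with 30% at both levels. The stated value is 0.27.

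**Internal check against the fallback.** With centres and assumptions unchanged, halving N can at most double the variance, so the MDES can rise by at most sqrt(2) = 1.41. The stated rises are 0.405/0.262 = 1.55 and 0.341/0.2221 = 1.54. The two ranges therefore cannot share the same assumptions, whichever multiplier is used. At N = 640 the formula gives 0.364 without covariates, 0.3415 with 30% at individual level and 0.305 with 30% at both levels. The stated 0.341 matches the individual-level case, but 0.405 matches none. Losing 8% can raise an MDES by at most sqrt(1/0.92) = 1.043, yet the fallback moves from 0.341 to 0.404 (a ratio of 1.18) when covariates and attrition are combined. The formula gives 0.310 to 0.346 there.

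**The case against.** The strongest points on the other side are these.

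- **Not every input is fixed.** The level of the 30% is missing, so the adjusted MDES is a range. This stands, and is why a range is given. The no-covariate figure is fully determined.
- **0.262 alone is close to the most favourable adjusted case.** With 30% explained at both levels, power at 0.262 is 77% (t) or 82% (normal). But 0.262 is the larger end of the range, so it must be the no-covariate value, and 0.2221 would still be unexplained.
- **The limit argument is narrow under the normal approximation.** It misses 0.262 by only 0.002 and does not exclude 0.2221. This stands, but that approximation is generous with 16 degrees of freedom, and the calculation at N = 1280 settles the matter without the limit.
- **The attrition figure of 0.27 may be nearly right.** It is close to 0.275, the both-levels case. The sentence does not name its case, so the defect here is partly one of labelling.
- **A one-sided normal calculation gives 0.271 and 0.227.** These are near the stated pair but not equal to it, and the protocol specifies two-tailed tests.
- **The adequacy conclusion may survive.** It is argued against pilot effects that the document does not give. If those were above about 0.33, the conclusion could still hold, but it would need to be argued against the corrected figures.

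Balancing the randomisation on centre characteristics might also remove some between-centre variance, but the protocol claims no gain beyond the 30%.

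**Conclusion.** The concern holds. From the protocol's own inputs, the MDES at 80% power is 0.325 without covariates, against 0.262 stated. With covariates it is 0.272 to 0.313, against 0.2221 stated. The risk of missing an effect of the stated size is about 38% at 0.262 without covariates and 37% to 49% at 0.2221 with them, rather than 20%. The covariate label is reversed, and the full-sample and fallback ranges are mutually inconsistent.

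These results assume equal centre sizes and 16 degrees of freedom. The normal approximation narrows the gap but does not close it. The experimental design section makes recruitment proportional to centre size, so sizes will differ. With an assumed coefficient of variation of 0.3 to 0.5, the no-covariate MDES would be 0.336 to 0.355.

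**What to change.** Rewrite the MDES paragraph as follows.

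1. **Full sample:** 0.325 without covariates; with covariates, 0.313 if the 30% applies at individual level only, or 0.272 if it applies at both levels.
2. **After 8% attrition:** 0.329 without covariates; 0.315 or 0.275 with them.
3. **Labels:** state that the smaller value is the covariate-adjusted one, name the level at which the 30% is assumed, and say which case the attrition figure describes. If the level is individual, as the fallback's 0.341 suggests, the matching full-sample figure is 0.313.
4. **2018-only fallback:** 0.364 without covariates and 0.3415 or 0.305 with them; after attrition with covariates, 0.346 or 0.310.
5. **Adequacy sentence:** restate it against these values and give the pilot effect sizes on which it relies.

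The cost is the wording of one paragraph and a less favourable stated MDES. The sample, allocation and conduct of the trial do not change.
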